| |  | Not using HIPAA-protected information for any research activities |
| |  | Through a HIPAA Authorization signed by the participant (or their legally authorized representative). |
| |  | Requesting that the IRB approve a waiver of authorization in this application. Submit HRP-209 – FORM – UC Waiver of HIPAA Authorization |
| |  | As a limited data set under a data use agreement. |
| | 30.1 FDA – Select all that apply. | |
| 30.0 STUDY INTERVENTION/ INVESTIGATIONAL AGENT |  | Drugs/Biologics |
| | The proposed research involves the administration of an article (e.g. drug, biologic, herbal preparation, dietary supplement, etc.) to a human where the article is intended for use in the diagnosis, cure, mitigation, treatment, or prevention of disease or is intended to affect the structure or any function of the body. For both FDA and non-FDA approved article. Include HRP-306 – | |

TEMPLATE: RESEARCH PROTOCOL

| NUMBER | ACTIVE DATE | PAGE |
|---------|-------------|----------|
| HRP-503 | 02-04-2020 | 34 of 44 |

| | | |
|---|------------------------|--|
| | | WORKSHEET Drugs and Biologics in the submission in RAP. |
|  | Devices | Any research that involves the use of a device (medical or other devices, approved or investigational) to test the safety or effectiveness of the device or the device is the focus of the research. Note: This includes research that will use human samples to test the safety or effectiveness of a device. Include HRP-307 – WORKSHEET Devices in the submission in RAP. |
|  | Data Collection | Any research that involves the collection of data or other results from individuals that will be submitted to, OR held for inspection by, the FDA. In general, this would include research that involves any data that will be provided (in any form) to a pharmaceutical, medical device or biotech company. |
|  | Specimens | Any research activity where specimens (of any type) from individuals, regardless of whether the specimens are identifiable, are used to test the safety or effectiveness of any device (medical or other devices, approved or investigational) and the information will be submitted to, or held for inspection by, the FDA. |
|  | Not Applicable | None of the above describes my research. |
| 30.2 Describe the study intervention and/or investigational agent (e.g. drug, device) that is being evaluated. | | |
| Not Applicable | | |
| 30.3 Drug/Device Handling: Describe plans to store, handle, and administer those drugs or devices so that they will be used only on subjects and be used only by authorized investigators. | | |
| Not Applicable | | |
| 30.4 If the drug is investigational and has an IND or if the device has an IDE, or claim of an abbreviated IDE (non-significant risk device) include the information below: | | |
| 
 Identify the holder of the IND/IDE/Abbreviated IDE Explain the procedures followed to comply with the sponsor requirements for FDA regulated research (as applicable, 21 CFR 11, 21 CFR 54, 21 CFR 210, 21 CFR 211, 21 CFR 312, 21 CFR 812, 21 CFR 820) If the PI holds the IND/IDE, please include the FDA Application and the FDA Letter of Acknowledgement on the Drugs/Devices page of the RAP Smart Form. Please also note that a Safety Monitoring Plan will be required if the PI holds the IND/IDE. | | |
| Not Applicable | | |

| | | | |
|--|---|-------------|----------|
| 
31.0 ADDITIONAL REVIEWS AND CONSIDERATIONS
 | 
31.1 Check all that apply.
 
 The proposed research meets the definition of a clinical trial, is regulated by HHS, and requires that the consent form is posted to a federal website within 60 days of completion Clinical Trial: A research study in which one or more human participants are prospectively assigned to one or more interventions (which may include placebo or control) to evaluate the effects of those interventions on health-related or behavioral outcomes.
 
 The proposed research involves embryonic stem cells or xenotransplantation.
 
 The PI is responsible for registration of this study on www.clinicaltrials.gov. (Please contact the Human Research Protection Program with questions about clinicaltrials.gov)
 
 The proposed research requires review by the Institutional Biosafety Committee (IBC). IBC review is required for research that will utilize infectious agents, select agents, recombinant DNA or viral gene transfer vectors, toxins for human gene transfer or genetically modified agent.
 
 The proposed research requires Radiation Safety Committee (RSC) review. RSC review is required if the research involves participants being exposed to radiation for research purposes or an increase in frequency or duration of radiological imaging procedures.
 
 UC Student is serving as Principal Investigator (Add the Faculty Advisor to the Study Team Members page in the RAP Smart Form and ensure that their CV is included in their RAP profile.)
 
 UC study team members will be conducting research activities at international location(s). If the research involves international locations, describe additional safeguards included to protect the rights and welfare of subjects recruited in these locations. Refer to HRP-399 – MEMBER WORKSHEET International Research for more information on the information required for review for international studies.
 
Description, e.g. information about local research oversight, local context, etc.
 
 Collection of information that may include incriminating activities (e.g. illicit drug use, illicit sexual behaviors, fraudulent behaviors, theft, abortion or other related activities that may be illegal in some states, assault)
 | | |
| | NUMBER | ACTIVE DATE | PAGE |
| | HRP-503 | 02-04-2020 | 35 of 44 |
| | | | |
| | | | |
| | | | |
| | | | |
| | | | |
| | | | |
| | | | |

TEMPLATE: RESEARCH PROTOCOL

NUMBER

ACTIVE DATE

PAGE

HRP-503

02-04-2020

36 of 44

| | | | | | | |
|---|---|--|--|---------------------------------------|-------------------------------------|--|
|  Review of UC Student records without obtaining consent. If so, a FERPA waiver is required. (Please reach out to [name] with UC Office of General Counsel.)  Sharing of genomic information generated from NIH-funded research  UC Health services will be utilized (check applicable). 
 
  Investigational Drug Services	 Imaging Services	 Lab Services	
 
  CCHMC Services will be utilized (check applicable). 
 
  CICRL	 IRC	 SRC	
 
  Acute Care Research (Research that occurs within 24 hours of a visit to an emergency department or unscheduled admission, or within 24 hours of identification of a new or worsening condition – characterized by sudden onset requiring immediate care)  The research team will send data FROM the United States TO another country: if so, list the country or countries here  The research team will send data FROM another country TO the United States: if so, list the country or countries here |  Investigational Drug Services |  Imaging Services |  Lab Services |  CICRL |  IRC |  SRC |
|  Investigational Drug Services |  Imaging Services |  Lab Services | | | | |
|  CICRL |  IRC |  SRC | | | | |
| | | | | | | |
| | | | | | | |
| | | | | | | |
| | | | | | | |
| | | | | | | |
| | | | | | | |
| | | | | | | |
| | | | | | | |

| | | | |
|----------------------------------|--|--|--|
| 32.0 REGULATORY OVERSIGHT | 32.1 Check the applicable federal oversite and/or funding. | | |
| |  Environmental Protections Agency |  Department of Energy | |
| |  Tribal Law |  Department of Defense | |
| |  Department of Justice |  Department of Education | |
| |  Food and Drug Administration |  Health and Human Services (NIH) | |
| |  Office of Civil Rights |  National Science Foundation | |
| |  Veterans Affairs *See Below |  Other Federal Agency | |
| |  *Check if you will enroll non-veterans |  ICH-GCP (E6) | |
| |  Specify other federal agency/oversight Name | | |

| | | | |
|---------------------|---|--|--|
| 33.0 SETTING | 33.1 Where will research activities take place, including where data will be stored/accessible (check all that apply). | | |
| |  Barrett Cancer Center |  Infectious Disease Clinic (Holmes-UC Health) | |
| |  Blue Ash Campus |  Kettering Laboratory | |

TEMPLATE: RESEARCH PROTOCOL

| | | |
|--------|-------------|------|
| NUMBER | ACTIVE DATE | PAGE |
|--------|-------------|------|

| | | |
|---------|------------|----------|
| HRP-503 | 02-04-2020 | 37 of 44 |
|---------|------------|----------|

| | | | |
|-------------------------------------|--|--------------------------|--|
|  | Cincinnati State Technical and Community College |  | Linder Center of Hope |
|  | Clermont College |  | Liver Transplant Clinic (Medical Arts Building) |
|  | College of Allied Health Sciences |  | Medical Sciences Building |
|  | College of Arts & Sciences |  | Shriners Hospital |
|  | College of Business |  | Talbert House |
|  | College Conservatory of Music |  | UC Gardner Neuroscience Institute |
|  | College of Design, Art, Architecture & Planning |  | UCMC (Emergency Department, Inpatient and Outpatient Units) |
|  | College of Education |  | UCMC NICU |
|  | College of Nursing |  | University of Cincinnati Physicians (UCP) |
|  | College of Pharmacy |  | University Pointe Surgical Hospital |
|  | Crossroads Center |  | VA – Cincinnati Medical Center |
|  | Drake Center |  | VA – Chillicothe Medical Center |
|  | Genome Research Institute (Reading Campus) |  | VA – Columbus Medical Center |
|  | Hoxworth: Inpatient Unit |  | West Chester Hospital |
|  | Hoxworth: Outpatient Clinics |  | Other UC/UC Health Affiliated location/clinic: list location/clinic |

| | |
|--------------------------------|--|
| 34.0 EXTERNAL LOCATIONS | 34.1 List any external locations to UC or its affiliates. |
| | External institutions with collaborators: Cincinnati Children's Hospital Medical Center, Every Child Succeeds. CCHMC IRB will also be conducting their own review of this study. |

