| | 
We do not anticipate difficulty with reaching adequate study enrollment given the number of eligible participants significantly exceeds the number of participants required for this pilot trial (i.e., approximately 400 families will enroll in ECS during the 6-month recruitment period and only 30 families are required for study enrollment). Our team has a successful track record of enrollment of ECS families into supplemental intervention trials. However, it is possible we may encounter participant attrition. We will take several safe guards to reduce attrition. All intervention and study visits will be conducted in participants' homes to reduce barriers to attendance. Multiple methods for contacting families will also be obtained, including contact information for friends and family members who are likely to know the location of participants should they be temporarily out of contact. Regarding the GLA phase, GLA and action planning sessions will be scheduled at times likely to be convenient to participants, such as evenings and weekends, and if we encounter recruitment challenges, we could conduct multiple GLA sessions to meet participant availability.
 |
| | 
3.2 Describe the time that you will devote to conducting and completing the research, i.e. percent effort.
 
PI will have 15% effort on this project.
 |
| | 
3.3 Describe the availability of medical or psychological resources that subjects might need as a result of an anticipated consequences of the human research.
 |
| | 
The intervention tested in this study (HEMI) is trauma-informed and includes trauma-specific treatment components if participants have a significant trauma history. This is because stress and trauma can have a significant impact on feeding and eating, and we know rates of trauma are high in our target enrollment population. The research study
 |

TEMPLATE: RESEARCH PROTOCOL

| NUMBER | ACTIVE DATE | PAGE |
|---------|-------------|---------|
| HRP-503 | 02-04-2020 | 9 of 44 |

interventionists are graduate students in Clinical Psychology and trained in discussion and treatment of trauma. However, families may feel uncomfortable talking about these topics, and our research study can provide psychological referral resources if families would like that information.

3.4 Describe your process to ensure that all persons assisting with the research are adequately informed about the protocol, the research procedures, and their duties and functions.

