Participants will complete home-based baseline and post-treatment study visits when the child is 2 months and 9 months of age. Families randomized to the intervention condition will participate in six treatment sessions delivered as monthly 1-hour home or virtual visits based on the desires, interests, and needs of families, when the child is 3, 4, 5, 6, 7, and 8 months of age in addition to participation in the standard ECS visits. Given the program's target of behavior change and use of behavioral strategies, interventionist-delivered HEMI sessions will be provided by advanced clinical psychology doctoral students (supervised by a licensed clinical psychologist, PI [name]) accompanied by support staff. Two peer counselor-led sessions will be delivered as 1-hour home or virtual visits, based on the desires, interests, and needs of families and peer counselors, when the child is 5 and 8 months of age. Families in the control condition will receive the standard ECS content and complete baseline and post-treatment visits.

6.3 Describe procedures being performed to monitor subjects for safety or minimize risks.

Based on the size ($n = 30$) and complexity of the trial (e.g., unblinded trial) and the minimal risk of the study intervention to participants, this study will utilize an independent safety monitor (ISM) whose primary purpose will be to provide guidance regarding adverse events and safety issues. The ISM will be a medical expert (e.g., pediatrician, nurse) who is independent of the study and able to provide external and unbiased evaluation through consultation pertaining to safety issues. This person will be available in real-time on an as-needed basis should any concerns regarding adverse events or other safety issues arise. The ISM will be identified during the study start-up phase. The ISM will review relevant participant safety data and make recommendations regarding continuation, modification, or termination of the trial due to safety risk. Communication with the ISM will occur on an as-needed basis when safety concerns arise as well as annual meetings with the study PI to discuss overall trial safety data.

TEMPLATE: RESEARCH PROTOCOL

| NUMBER | ACTIVE DATE | PAGE |
|---------|-------------|----------|
| HRP-503 | 02-04-2020 | 13 of 44 |

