The following potential adverse events will be assessed throughout the study period: occurrence of choking episodes during infant feedings (at each study visit and interventionist-led treatment session), growth faltering (monitored at each interventionist-led treatment session for infants in the treatment condition; length and weight will be monitored for all participants [i.e., treatment and control] at baseline and post-treatment), and unexpected adverse events.

Study participants will be informed of any changes to the known risks and benefits of participating in the current study, including if it is identified that treatment participants are at greater risk for adverse events. If participants in the treatment arm experience greater adverse events, possible discontinuation of the study or modification of the intervention will be considered under the guidance of the ISM.

6.5 Where applicable, list and describe the data collection tools such as surveys, data collection forms, etc. All tools described should be uploaded in the RAP Smart Form on the Local Site Documents page unless they are standardized, validated tools.

Demographics Form. Participants in both the intervention and GLA methodologies will complete a demographics form. There is a separate demographic form for each of these methodologies because the interventionist participants will be asked additional demographic details about their participating child, while GLA participants will only report their own adult demographics.

Maternal Feedback on Intervention: Maternal Feedback on the Intervention will be obtained through a quantitative survey and a qualitative interview. The quantitative survey consists of Likert scale ratings on whether they perceived the intervention as suitable, occurring at the right time, being presented clearly, and helpful; mothers will also rate satisfaction with the intervention and their confidence in implementing the recommendations made by the study team. Qualitative interviews will be conducted with each family by a research staff member who was not the study interventionist (to prevent potential bias) to obtain feedback regarding additional information that would be helpful to add to the program, content that was not helpful and could be eliminated from the program, other changes they would like to see to the program, and aspects they would like to see stay the same about the program.

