| 8.0 SHARING OF RESULTS WITH SUBJECTS | 7.3 Describe the procedures to release data or specimens, including: (the process to request a data/specimen release, approvals required for release, who can obtain data or specimens, and the data to be provided with the specimens. |
| | Data will only be available to members of the study research team. |
| 9.0 STUDY TIMELINES | 8.1 Describe whether results (study results or individual subject results, such as results of investigational diagnostic tests, genetic tests, or incidental findings) will be shared with subjects or others (e.g., the subject's primary care physician) and if so, describe the process for sharing. If you do not intend to share any results, please state that here. |
| | Results will not be shared with participants or any of their medical providers. |
| 9.0 STUDY TIMELINES | 9.1 Describe the duration of an individual subject's participation in the study. List the number of study visits or frequency of study visits. |
| | For Aim 1, participants who participate in the GLA only will be in the study for 1 visit on one day. If participants choose to participate in the optional Action Planning session, they will do 2-3 visits over the course of approximately 2 months. |
| | For Aim 2, individual subjects will be in the study for approximately 8 months. Depending on randomization, participants will either complete 2-3 total visits at the beginning and end of the 8-month timeline or complete 8 monthly visits. |
| | 9.2 Describe the timeline allotted for the enrollment of subjects. |
| | Subjects will be enrolled during the first year of grant funding. |
| | 9.3 Describe the estimated date for the investigators to complete this study (complete primary analysis). |
| | Data collection for this study will span 24 months, with the projected start date of January 2021. Primary analysis will be completed within a year of the last data collected for the current project. |

TEMPLATE: RESEARCH PROTOCOL

NUMBER

HRP-503

ACTIVE DATE

02-04-2020

PAGE

16 of 44

| | | | |
|--|---|--|--|

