18.3 How will the safety information will be collected?

Adverse event data collection sheets have been established for recording adverse events reported by participants. These forms will be completed at each treatment session (i.e., Session 1, Session 2, Session 4, Session 5, and Post-Treatment) or study visit conducted by a research staff interventionist (i.e., not done at peer counselor-led sessions). For choking episodes, the date of the episode, details of the episode (e.g., food being eaten, situation in which eating occurred), and any intervention required (e.g., medical attention) will be recorded. For growth faltering, caregivers will be asked to describe their concerns regarding their child's growth. Additionally, infant weight will be recorded at each study visit and treatment session (i.e., Session 1, Session 2, Session 4, Session 5, and Post-Treatment) conducted by a research staff interventionist (i.e., not done at peer counselor-led sessions). All other potential adverse events reported to study staff will also be documented.

18.4 The frequency or periodicity of review of cumulative data.

Regularly scheduled meetings between the ISM and PI will occur annually. Emergency meetings will be scheduled by the PI if immediate concerns arise between regularly scheduled meetings.

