18.5 Who will review the data?

An independent safety monitor (ISM) will be identified during the start-up phase of the study timeline and will provide guidance regarding adverse events and safety issues.

18.6 The statistical tests for analyzing the safety data to determine whether harm is occurring.

ANOVAs will examine the number of adverse events in the control versus intervention group.

18.7 Any conditions that trigger an immediate suspension of research.

Study participants will be informed of any changes to the known risks and benefits of participating in the current study, including if it is identified that treatment participants are at greater risk for adverse events. If participants in the treatment arm experience greater adverse events, possible discontinuation of the study or modification of the intervention will be considered under the guidance of the ISM. Any action resulting in temporary or permanent suspension of the study will be immediately reported to the funding agency program official.

| NUMBER | ACTIVE DATE | PAGE |
|---------|-------------|----------|
| HRP-503 | 02-04-2020 | 24 of 44 |

| | |
|--|--|
| 19.0 PARTICIPANT PRIVACY | 19.1 Describe the provisions to protect participants' privacy and to minimize the intrusiveness of the study questions or procedures. |
| | Participant responses will be linked to their study ID # rather than their names. Only study staff will have access to the file linking study ID# and names. All identifying information as defined by the HIPAA Privacy rule will be removed (e.g., birthdates) 2 years after the research ends. Study staff will also receive training on information related to confidentiality and session content management. This training includes education about treatment content (e.g., responsive feeding, infant obesity risk factors) and specific treatment recommendations, strategies for active listening, skills for asking sensitive questions, and how to manage sensitive/confidential information. |
| 20.0 COMPENSATION FOR RESEARCH RELATED INJURY | 20.1 For more than minimal risk research, describe the available compensation in the event of research-related injury. |
| | Not applicable. |
| 21.0 ECONOMIC BURDEN TO SUBJECTS | 20.2 Provide a copy of contract language relevant to compensation for research-related injury. |
| | Not Applicable |
| 21.0 ECONOMIC BURDEN TO SUBJECTS | 21.1 Describe any costs that subjects may be responsible for because of participation in the research. |

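### Section 18.6 compares adverse event counts between arms, but after baseline the event form is scheduled five times in the intervention arm and once in the control arm

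*Protocol*

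**What the plan says.** Protocol 18.6, on statistical tests for the safety data, reads in full: "ANOVAs will examine the number of adverse events in the control versus intervention group". It gives no rate, common look-back period, restriction to shared visits, or timing. The SAP does not mention adverse events.

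On collection, 18.3 says "These forms will be completed at each treatment session (i.e., Session 1, Session 2, Session 4, Session 5, and Post-Treatment". The same section adds study visits run by interventionist staff and excludes peer counselor-led sessions. Section 6.2 places the six treatment sessions at 3 to 8 months of age, with the peer-led ones at 5 and 8 months. For the other arm, 6.2 says "Families in the control condition will receive the standard ECS content and complete baseline and post-treatment visits"; those visits are at 2 and 9 months.

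Section 6.3 shows the same pattern. Choking is asked about at study visits and interventionist-led sessions, and growth faltering is "monitored at each interventionist-led treatment session for infants in the treatment condition", with length and weight taken in both arms at baseline and post-treatment.

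On use of the data, 18.7 says "If participants in the treatment arm experience greater adverse events, possible discontinuation of the study or modification of the intervention will be considered"; the independent safety monitor advises on that decision. Section 18.4 adds "Regularly scheduled meetings between the ISM and PI will occur annually", with emergency meetings if needed.

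**The concern.** A raw count depends on how often events occur and on how often someone asks about them. Here the second factor differs by arm by design. An intervention mother looks back one or two months at each enquiry, whereas a control mother looks back seven. If any mild choking episode or growth concern is forgotten over the longer interval, the intervention arm shows more events even when the true rates are equal.

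During the trial the imbalance needs no assumption about recall. Until a control infant reaches 9 months, no enquiry after baseline is scheduled for that infant, while an intervention infant may already have had four.

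At stake is the only between-arm safety comparison in the plan. As written, it cannot separate a true excess from unequal enquiry, and 18.7 allows greater adverse events in the treatment arm to prompt consideration of discontinuing the study or modifying the intervention.

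**Working it through.** The plan states no error rate or expected count for this comparison, so there is no figure to reproduce. The schedule comes first, then two illustrations whose assumptions are mine.

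**1. Schedule (documented).** Sessions at 3, 4, 5, 6, 7 and 8 months, less the peer-led sessions at 5 and 8, leave Sessions 1, 2, 4 and 5 at 3, 4, 6 and 7 months. Adding the 9-month visit:

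| Arm | Forms after baseline (age, months) | Number | Look-back (months) |
|---|---|---|---|
| Intervention | 3, 4, 6, 7, 9 | 5 | 1, 1, 2, 1, 2 |
| Control | 9 | 1 | 7 |

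Sessions may be virtual, and weight is measured only in person (6.5), so a virtual session may add no weighing. The main route for the bias is more frequent asking.

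**2. End of trial, equal true rates.** Assume an event at age t is reported at the next enquiry with probability exp(−ln 2 × (next enquiry − t) / half-life). Averaging over t gives the captured fraction.

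| Assumed half-life (months) | Events uniform over 2–9 months: intervention v control | Ratio | Events at 6–9 months: intervention v control | Ratio |
|---|---|---|---|---|
| 2 | 0.774 v 0.376 | 2.06 | 0.763 v 0.622 | 1.23 |
| 3 | 0.840 v 0.496 | 1.70 | 0.831 v 0.721 | 1.15 |
| 6 | 0.915 v 0.686 | 1.33 | 0.910 v 0.845 | 1.08 |
| 12 | 0.956 v 0.823 | 1.16 | 0.953 v 0.918 | 1.04 |

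With perfect recall and equal detection the ratio is 1.

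**3. Chance of a significant false excess.** Assumptions: 15 infants per arm, Poisson events at the same true rate in both arms, half-life 3 months, uniform timing. The test is a two-group ANOVA at two-sided 0.05, counting only results with the intervention arm higher. (The SAP gives 0.05 for Aim 2 analyses; 18.6 gives no level.) At 0.2 events per infant the expected recorded totals are 15 × 0.2 × 0.840 = 2.5 and 15 × 0.2 × 0.496 = 1.5.

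| True events per infant | Current plan | Full equal capture | 9-month enquiry only, both arms |
|---|---|---|---|
| 0.1 | 1.3–1.4% | 1.1% | 0.2–0.3% |
| 0.2 | about 5% | 2.2% | 1.1% |
| 0.5 | about 11.6% | 2.4% | 2.4% |

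The fair comparator for bias is the full-capture column. The last column is lower partly because fewer events enter the test. At 0.2 events per infant, the current plan records more events in the intervention arm in 60% of trials and fewer in 22%.

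**4. During the trial.** The timing of any review of counts by arm is not stated, so this too is illustrative. Section 3.1 says "approximately 400 families will enroll in ECS during the 6-month recruitment period", and 5.1 starts Aim 2 in June 2021. Assume even enrolment of 15 per arm over six months from then, with all visits attended. Covered time is the time from baseline to the last scheduled enquiry reached, with enquiries at 1, 2, 4, 5 and 7 months after baseline (intervention) or 7 months (control).

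At month 7, follow-up is uniform between 1 and 7 months. Intervention coverage is 15 × (1×1 + 2×2 + 1×4 + 2×5)/6 = 47.5 of 15 × 4 = 60 infant-months; control coverage is 0 of 60. At month 12, infants enrolled in the first five months have had the 9-month visit. Intervention coverage is 15 × (5×7 + 1×5)/6 = 100 and control coverage is 15 × (5×7)/6 = 87.5.

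| Months after June 2021 | Intervention v control, covered infant-months |
|---|---|
| 7 | 47.5 v 0 |
| 8 | 62.5 v 17.5 |
| 10 | 87.5 v 52.5 |
| 12 | 100 v 87.5 |
| 13 | equal |

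If enrolment took 12 months, the figures would be 23.8 v 0 at month 7 and 67.5 v 43.8 at month 12.

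**The case against.** Several passages might seem to even out the schedules, but none does. Section 15.1 says these risks are monitored at every study contact, but the intervention arm has more contacts. Section 9.1 says "participants will either complete 2-3 total visits at the beginning and end of the 8-month timeline or complete 8 monthly visits"; a third control visit, which is not explained, would narrow the gap without closing it. Section 18.3 also documents events reported spontaneously, so the control count need not be zero before 9 months, but such reports are unscheduled.

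The stronger objections concern consequence, and much of them stands. The study is minimal risk, and the safety monitor is an independent medical expert who can judge individual events: the choking form records the date, circumstances and any intervention required. Section 18.7 does not refer to the ANOVA, and no automatic rule acts on the count. Asking more often in the intervention arm also errs towards noticing harm there, and the 9-month comparison gives up some of those events.

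Two stronger readings are tempting. A reader might infer that the ANOVA will be run at annual meetings against a control arm not yet asked. The documents do not say so; 18.6 gives no timing, and 47.5 v 0 depends on an assumed meeting date. A reader might also infer that a significant false signal is likely, or that the 9-month comparison cuts it from about 5% to 1.1% by removing bias. It is uncommon under most of these assumptions, and part of that fall is lost information.

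**Conclusion.** The point holds as a flaw in the comparison. The five-to-one schedule follows directly from 6.2, 6.3 and 18.3, and neither document puts the two counts on a common basis. The direction follows too: with equal true rates, the intervention arm is expected to show more recorded events unless seven-month recall is perfect and detection is equal.

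The size cannot be determined from the documents. The end-of-trial ratio lies anywhere from 1.0 to about 2, depending on recall and on when events occur, and the false-excess rates also depend on the assumed event rate. Any imbalance in a review during the trial depends on its date and on whether counts by arm are examined at all.

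This should be corrected because 18.6 is the only between-arm safety comparison given and the correction is cheap. It is not evidence that the trial would be stopped wrongly or that the monitoring itself is inadequate.

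**What to change.** In 18.6, base the between-arm comparison on events elicited identically in both arms at the 9-month visit: the same form, the same question covering the period since the baseline visit, and the weight and length already measured in both arms. If the comparison is shown before all those visits are complete, limit it to infants of either arm who have had theirs.

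Alongside it, keep a descriptive table of all events by arm and by the visit at which they were elicited. Give the number of completed enquiries per arm and a note that total counts come from unequal enquiry. State in 18.6 and 18.7 that the safety monitor receives both, plus all individual events. Monitoring, the monitor's discretion and the choice of test are unchanged.

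The cost is protocol wording and one question on an existing form at an existing visit. Three downsides should be stated as limitations:

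- The formal comparison uses fewer intervention-arm events: about 50% captured instead of 84%, at an assumed 3-month half-life.
- It is unavailable until 9-month visits begin, so earlier reviews rest on individual events and the descriptive table.
- Earlier questioning may still aid recall in the intervention arm. If it preserved a quarter of the events otherwise forgotten, capture would be 0.496 + 0.25 × (0.840 − 0.496) = 0.582 and the residual ratio 0.582/0.496 = 1.17. If it preserved half, capture would be 0.668 and the ratio 1.35. Both are below the 1.70 under the current plan.
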